## 2.0 Objectives\*

- 2.1 A randomized controlled trial is planned to evaluate a brief, web-based intervention intended to educate about tonic immobility (TI) within a sample of those who experienced TI in the context of a traumatic event.
- 2.2 It is hypothesized that the TIP intervention will show benefits in a sample of those who have experienced a traumatic event. Specifically, we hypothesize that: TIP will significantly reduce feelings of posttraumatic feelings of guilt and shame compared to control; TIP will significantly reduce PTSD symptoms across time relative to control; reduction in trauma-related guilt and shame will mediate the association between condition and changed in PTSD symptoms at follow-up.

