## PROTOCOL TITLE: Development and Evaluation of a Tonic Immobility Focused Psychoeducational Intervention - RCT

6.2 The study proposes to enroll 120 participants to test the efficacy of the TIP intervention, compared to a HET control condition. All data collection will be conducted using Qualtrics. The study will be comprised of a total of three time points: Baseline, Week 1 follow-up, and Month 1 follow-up.

First, eligible participants will read and sign an informed consent that outlines all study procedures, details limits to confidentiality, and emphasizes that participants may discontinue participation at any time with no penalty.

The first appointment, baseline, will include pre-intervention self-report measures, the completion of one of the two interventions (TIP or PHET), and post-intervention self-report measures. The baseline appointment is expected to take 90 minutes. Participants will be compensated with a \$30 gift card or 1.5 course credits. All baseline procedures will be conducted either in-person within the Anxiety and Behavioral Health Clinic research suite or virtually via HIPAA-compliant Zoom. For in-person sessions, all COVID-19 related federal, state, and local guidelines as well as FSU IRB regulations will be followed. See section 6.3 for further information on COVID-19 safeguards.

The second and third appointments, week 1 and month 1 follow-up, will be completed online. Participants will be contacted via email and asked to complete a battery of self-report measures via a Qualtrics survey link. The questionnaire is expected to last 30 minutes and participants will be compensated either a \$10 gift card or 0.5 course credits for the completion of each appointment.

After the completion of the month 1 follow-up appointment, participants will be debriefed and individuals in the control condition will be given the opportunity to receive the active treatment condition.

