**17.0 Data Management\* and Confidentiality**

**17.1** *Describe the data analysis plan, including any statistical procedures or power analysis.*

Preliminary analyses and data screening will be conducted prior to the primary analyses. This will include checking equivalence of random assignment to treatment condition based on key baseline characteristics. Specifically, analyses will be conducted to ensure that there are not baseline differences between condition (active vs. control) in terms of age, gender, and TIQ total scores.

Hierarchical linear regression analyses will be conducted to examine the impact of intervention condition on early treatment outcomes including posttreatment guilt, posttreatment shame, and week 1 PTSD symptoms. Analyses will be conducted in SPSS version 27.0.

Latent difference score analyses will be utilized to examine the differential change in guilt, shame, and PTSD symptoms between intervention conditions, across all study timepoints. Analyses will be conducted in Mplus version 8.0 (Muthén & Muthén, 1998-2017). Full information maximum likelihood (FIML) with the adjusted Yuan-Bentler scaled chi-square index (Y-B  $\chi^2$ ) will be utilized when possible in order to account for missing data. To determine model fit, the S-B  $\chi^2$  statistic as well as several indices will be used.

Three separate models will be estimated for the impact of treatment condition on guilt, shame, and PTSD symptoms. The effects of treatment condition on changes in guilt from pre-intervention to post-intervention (change 1), from post-intervention to week 1 (change 2), and from week 1 to month 1 (change 3) will be examined using a multi-group latent difference score (LDS) approach (Mun et al., 2009). The same methods will be used to examine effects of treatment condition on shame from pre-intervention to post-intervention (change 1), from post-intervention to week 1 (change 2), and from week 1 to month 1 (change 3) and PTSD symptoms from pre-intervention to week 1 (change 1), and from week 1 to month 1 (change 2).

The indirect effects of treatment condition on PCL-5 scores at month 1 through week 1 guilt and shame will be examined in two separate

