## PROTOCOL TITLE: Development and Evaluation of a Tonic Immobility Focused Psychoeducational Intervention - RCT

mediation models. Maximum likelihood and percentile bootstrapped CIs (with 5,000 resamples) will be used (Hayes & Scharkow, 2013; Preacher & Hayes, 2004).

17.2 *Describe the steps that will be taken to secure the data (e.g., training, authorization of access, password protection, encryption, physical controls, certificates of confidentiality, and separation of identifiers and data) during storage, use, and transmission.*

All data will be coded by arbitrary participant numbers to ensure confidentiality and will be stored using password protected documents. Specifically, once the participant is consented, they will be assigned a unique study ID, which will be used instead of their name on subsequent surveys. The document linking participant names to study IDs will be recorded in a password-protected Microsoft Excel document, which will be stored on a password-protected server inside the Anxiety and Behavioral Health Clinic (ABHC) research suite. Only ABHC study staff (i.e., PI, graduate students, and project coordinators) who have been trained in data management procedures will be able to access the data via password.

17.3 *Describe any procedures that will be used for quality control of collected data.*

See 17.4

17.4 *Describe how data or specimens will be handled study-wide:*

Data entry personnel will download the data into a dedicated, password-protected computer database. Computer files will be maintained on the servers and backed up daily. Computers and databases will be password protected with independent passwords known only to the PI and data entry personnel. Other safeguards include: (a) ensuring that all project staff are well informed about regulations pertaining to confidentiality, (b) the use of ID numbers as opposed to names on all data forms, (c) utilizing computer-based assessments whenever possible.

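### The hypothesis 3 models take week 1 guilt and shame as mediators without stated control for baseline or week 1 PCL-5, so guilt or shame that only follows an early PTSD drop could be reported as its mediator

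*Combined protocol and SAP*

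**What the plan says.** Section 2.2 states the third hypothesis as "reduction in trauma-related guilt and shame will mediate the association between condition and changed in PTSD symptoms at follow-up". Section 17.1 tests it in two separate models, one for guilt and one for shame, described as "The indirect effects of treatment condition on PCL-5 scores at month 1 through week 1 guilt and shame". On estimation it says "Maximum likelihood and percentile bootstrapped CIs (with 5,000 resamples) will be used". No covariates are named for these models.

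The timing of the measures matters here:

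- **PTSD symptoms.** Section 17.1 models "PTSD symptoms from pre-intervention to week 1 (change 1), and from week 1 to month 1 (change 2"), so the first PTSD re-measurement is at week 1. Section 6.2 has each follow-up completed as one battery through an emailed survey link, so the week 1 PCL-5 and the week 1 mediator come from the same survey.
- **Guilt and shame.** Section 6.2 describes the baseline appointment as "pre-intervention self-report measures, the completion of one of the two interventions (TIP or PHET), and post-intervention self-report measures". Section 17.1 uses a post-intervention guilt and shame score in its latent difference score models. It also lists "posttreatment guilt, posttreatment shame, and week 1 PTSD symptoms" as the early treatment outcomes.

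The plan therefore allows for a PTSD effect by week 1 and holds a guilt and shame score that precedes it. The mediation models do not use that score.

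**The concern.** Hypothesis 3 is a claim about mechanism: guilt and shame fall, and PTSD symptoms fall as a result. Under the planned timing, any PTSD change in the first week has already occurred when the mediator is measured. That change can drive week 1 guilt or shame, and it carries forward into month 1 PCL-5. It is then a common cause of mediator and outcome that arises after randomisation. Randomisation does not protect against it, and pre-intervention covariates cannot remove it.

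A significant indirect effect would be read as support for the mechanism behind TIP, although the data would also be consistent with PTSD improving early and guilt following.

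**Working it through.** **Inputs from the documents.** N = 120 (sections 1.0 and 6.2), the mediator and outcome times above, and a percentile bootstrap. The plan gives no alpha, effect size, SD, correlation or power calculation, so it has no figure of its own to reproduce. Every path value below is an assumption.

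**Assumed model, with no effect of guilt on PTSD.** X = 1 for TIP, 60 per arm (the allocation ratio is not stated). P0, P1 and P2 are PCL-5 at pre-intervention, week 1 and month 1. G0, Gp and G1 are guilt at pre-intervention, post-intervention and week 1.

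- G0 = 0.5·P0 + noise (variance 0.75), with P0 of variance 1
- Gp = 0.7·G0 − g·X + noise (variance 0.51)
- P1 = 0.7·P0 − d·X + noise (variance 0.51)
- G1 = 0.5·Gp + r·P1 + noise (SD 0.6)
- P2 = 0.8·P1 + noise (SD 0.6)

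Within each arm P1 and P2 have variance 1, so effects are in SD units. The true indirect effect through guilt is zero.

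**Expected false indirect effect, d = 0.5, r = 0.4, g = 0.** The total effect on P2 is 0.8 × (−0.5) = −0.40. The condition-to-mediator path is a = −0.4 × 0.5 = −0.20.

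- *No covariates.* Cov(Gp, P1) = 0.7 × 0.7 × 0.5 = 0.245. Var(G1) = 0.25 + 0.16 + 2(0.5)(0.4)(0.245) + 0.36 = 0.868. Cov(G1, P2) = 0.8 × (0.5 × 0.245 + 0.4) = 0.418. So b = 0.418/0.868 = 0.482 and a·b = −0.096, which is 24% of the total effect.
- *With P0 and G0.* Residual Var(G1) = 0.25 × 0.51 + 0.16 × 0.51 + 0.36 = 0.569. Residual Cov(G1, P2) = 0.8 × 0.4 × 0.51 = 0.163. So b = 0.287 and a·b = −0.057, or 14% of the total.

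The simulated means were −0.095 and −0.055.

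**How often mediation is declared.** Each setting used 400 simulated trials with 500 percentile-bootstrap resamples per trial (the plan specifies 5,000). A trial counts when the 95% interval lies wholly below zero, so the nominal rate is 2.5%. The simulation standard error at 20% is √(0.2 × 0.8/400) = 2 points.

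| d | r | g | Week 1, no covariates | Week 1 + baseline | Week 1 + baseline + week 1 PCL-5 | Post-intervention, no covariates | Post-intervention + baseline |
|---|---|---|---|---|---|---|---|
| 0.5 | 0.2 | 0 | 6.5% | 2.0% | 0% | 1.0% | 0% |
| 0.3 | 0.4 | 0 | 10.8% | 10.5% | 0.2% | 2.0% | 0% |
| 0.5 | 0.4 | 0 | 20.2% | 23.8% | 0% | 1.5% | 0% |
| 0.8 | 0.4 | 0 | 50.2% | 51.5% | 0% | 1.2% | 0% |
| 0.5 | 0.4 | 0.5 | 76.8% | 73.8% | 1.2% | 47.0% | 3.2% |

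**Reading the table.**

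1. Baseline covariates alone do not repair the week 1 model.
2. When g = 0, the near-zero rates for the post-intervention mediator carry little weight: TIP does not move that mediator, so its product of paths can hardly be significant. The last row is the fair test, because hypothesis 1 is that TIP lowers guilt and shame.
3. In the last row the post-intervention score without covariates still fails. There a = −0.5 and b = 0.8 × 0.245 = 0.196, so a·b = −0.098 (simulated −0.099), which comes entirely from shared baseline severity. With P0 and G0 in the model b = 0, and the simulated mean was −0.004.
4. These runs put week 1 PCL-5 in both equations. A separate simulation with other assumed paths put it in the outcome equation only and gave at most 1.9%.

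**Sensitivity to other assumed paths.** Further simulations gave about 3% to 38% for the baseline-adjusted week 1 mediator, and about 68% when TIP also lowers guilt. For the post-intervention mediator when TIP lowers guilt, they gave about 40% to 46% without covariates and about 2% to 5% with them.

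**When mediation is real but complete by week 1.** In two simulations where post-intervention guilt does drive week 1 PTSD, the week 1 mediator adjusted for week 1 PCL-5 detected it in about 1% and 3% of trials. The baseline-adjusted post-intervention mediator detected it in about 64% and 45%.

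**The case against.** The planned choice has a rationale. The week 1 mediator does precede the month 1 outcome, so a reader who inferred that mediator and outcome are measured together would be wrong; only the early part of the PTSD change coincides with the mediator. Guilt and shame are measured with a state scale (section 6.5), and a score taken just after the session may be transient, so preferring week 1 to capture lasting change is legitimate. The latent difference score models also show the early course of guilt, shame and PTSD. These points stand, but they do not answer the concern: those models treat each outcome separately and do not test mediation.

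Section 17.1 may simply have left covariates unlisted. That is possible, but the table shows that the usual pre-intervention covariates would not be enough for the week 1 mediator.

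Three stronger readings are tempting and are not supported:

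- *That false mediation will be reported.* The rate depends on unknown paths and falls to about 2% in one setting where PTSD weakly drives guilt.
- *That the two orders of events are equally likely.* Nothing in the documents allows their relative likelihood to be judged.
- *That the post-intervention score would settle the order.* The mediator-outcome path is not randomised, so unmeasured confounding remains with any mediator.

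**Conclusion.** The concern holds in a limited form. As written, the hypothesis 3 models leave out a plausible common cause of mediator and outcome, namely PTSD change up to week 1, and could credit guilt or shame with an effect it does not have. Under the assumed paths, false mediation ran from about 2% to 50% when TIP has no direct effect on guilt, and to about 70% or more when it also lowers guilt. These rates illustrate the risk and do not predict this trial's result: they rest on assumed early PTSD effects of 0.3 to 0.8 SD, an assumed PTSD-to-guilt path, and 1:1 allocation. The defect is confined to one mechanistic hypothesis. It gives no ground for doubting the randomised comparisons of guilt, shame or PTSD symptoms. The plan should be changed, but the trial does not depend on it.

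**What to change.** In section 17.1:

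1. Make post-intervention guilt and shame (baseline visit, after TIP or HET) the mediators of month 1 PCL-5. Put pre-intervention guilt or shame and pre-intervention PCL-5 in both the mediator and the outcome equations, and rest hypothesis 3 on this model. The covariates are essential; changing the time point alone is not a repair.
2. Keep the week 1 mediator model as supportive, with the same baseline covariates. Report it with and without week 1 PCL-5 in the outcome equation, and note that the adjusted version excludes mediation completed by week 1 and so is not an interchangeable test.
3. State that the mediator-outcome path is not randomised and that unmeasured confounding remains under every version.

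The cost is some wording and a few extra model runs on data already to be collected, with no added visit or participant burden. The downside is that post-session state scores may be more transient than week 1 scores, which is the reason to keep the week 1 model alongside.

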## PROTOCOL TITLE: Development and Evaluation of a Tonic Immobility Focused Psychoeducational Intervention - RCT

mediation models. Maximum likelihood and percentile bootstrapped CIs (with 5,000 resamples) will be used (Hayes & Scharkow, 2013; Preacher & Hayes, 2004).

17.2 *Describe the steps that will be taken to secure the data (e.g., training, authorization of access, password protection, encryption, physical controls, certificates of confidentiality, and separation of identifiers and data) during storage, use, and transmission.*

All data will be coded by arbitrary participant numbers to ensure confidentiality and will be stored using password protected documents. Specifically, once the participant is consented, they will be assigned a unique study ID, which will be used instead of their name on subsequent surveys. The document linking participant names to study IDs will be recorded in a password-protected Microsoft Excel document, which will be stored on a password-protected server inside the Anxiety and Behavioral Health Clinic (ABHC) research suite. Only ABHC study staff (i.e., PI, graduate students, and project coordinators) who have been trained in data management procedures will be able to access the data via password.

17.3 *Describe any procedures that will be used for quality control of collected data.*

See 17.4

17.4 *Describe how data or specimens will be handled study-wide:*

Data entry personnel will download the data into a dedicated, password-protected computer database. Computer files will be maintained on the servers and backed up daily. Computers and databases will be password protected with independent passwords known only to the PI and data entry personnel. Other safeguards include: (a) ensuring that all project staff are well informed about regulations pertaining to confidentiality, (b) the use of ID numbers as opposed to names on all data forms, (c) utilizing computer-based assessments whenever possible.

## 18.0 Provisions to Monitor the Data to Ensure the Safety of Subjects\*

*This section is required when research involves more than Minimal Risk to subjects.*

N/A

## 19.0 Provisions to Protect the Privacy Interests of Subjects

19.1 *Describe the steps that will be taken to protect subjects' privacy interests. "Privacy interest" refers to a person's desire to place limits on whom they interact or whom they provide personal information.*

## PROTOCOL TITLE: Development and Evaluation of a Tonic Immobility Focused Psychoeducational Intervention - RCT

All self-report data will be collected via Qualtrics, which is a secure website used by FSU to collect questionnaire data. Qualtrics data will be labeled only with participant IDs to ensure confidentiality. Data will be electronically communicated through password protected emails and password protected documents.

*19.2 Describe what steps you will take to make the subjects feel at ease with the research situation in terms of the questions being asked and the procedures being performed. "At ease" does not refer to physical discomfort, but the sense of intrusiveness a subject might experience in response to questions, examinations, and procedures.*

Study participants will be able to withdraw from participation at any point without penalty. Any distress that a participant may feel is expected to be brief in duration (i.e., few minutes). In addition, should any lasting feelings of distress arise from an individual's participation, study participants are encouraged to contact the study PI. Each prospective participant will be notified through the consent that identifying information will not be tied to survey responses, except for the signed consent form.

*19.3 Indicate how the research team is permitted to access any sources of information about the subjects.*

All research staff team will have access to password protected documents.

## 20.0 Compensation for Research-Related Injury

*20.1 If the research involves more than Minimal Risk to subjects, describe the available compensation in the event of research related injury.*

N/A

*20.2 Provide a copy of contract language, if any, relevant to compensation for research-related injury.*

N/A

## 21.0 Economic Burden to Subjects

*21.1 Describe any costs that subjects may be responsible for because of participation in the research.*

N/A

## 22.0 Consent Process

*22.1 Indicate whether you will be obtaining consent, and if so describe:*

This study will follow SOP: Informed Consent Process for Research HRP-090. The consent process will take place in-person in our research lab or via Zoom for participants taking part in the study

## PROTOCOL TITLE: Development and Evaluation of a Tonic Immobility Focused Psychoeducational Intervention - RCT

online. In the case of online participation, subjects will be asked to provide an electronic signature in place of their hand-written signature.

***Non-English Speaking Subjects - N/A***

***Waiver or Alteration of Consent Process (consent will not be obtained, required information will not be disclosed, or the research involves deception) - N/A***

***Subjects who are not yet adults (infants, children, teenagers) - N/A***

***Cognitively Impaired Adults - N/A***

***Adults Unable to Consent - N/A***

## 23.0 Process to Document Consent in Writing

***23.1 Describe whether you will be following “SOP: Written Documentation of Consent (HRP-091).” If not, describe whether and how consent of the subject will be documented in writing.***

This study will be following SOP: Informed Consent Process for Research HRP-091.

***23.2 If your research presents no more than minimal risk of harm to subjects and involves no procedures for which written documentation of consent is normally required outside of the research context, the IRB will generally waive the requirement to obtain written documentation of consent.***

N/A

***23.3 (If you will document consent in writing, attach a consent document. If you will obtain consent, but not document consent in writing, attach a consent script. Review “CHECKLIST: Waiver of Written Documentation of Consent (HRP-411)” to ensure that you have provided sufficient information. You may use “TEMPLATE CONSENT DOCUMENT (HRP-502)” to create the consent document or script.)***

See attached consent form.

## 24.0 Setting

***24.1 Describe the sites or locations where your research team will conduct the research.***

The research team will identify and recruit potential subjects from the FSU psychology undergraduate research pool and Tallahassee community. The research study will take place in person or online via HIPAA compliant Zoom. For in-person appointments, measures will be taken to safeguard against COVID-19 (e.g., social distancing, mask wearing, thoroughly cleaning surfaces).

## 25.0 Resources Available

### 25.1 Describe the resources available to conduct the research: For example, as appropriate:

- *Justify the feasibility of recruiting the required number of suitable subjects within the agreed recruitment period. For example, how many potential subjects do you have access to? What percentage of those potential subjects do you need to recruit?*

There are approximately **1,500** students screened through the undergraduate psychology research pool in 1 year and 159,426 people in the Tallahassee area. Thus, recruitment for our sample size ( $N = 120$ ) is highly feasible.

- *Describe the time that you will devote to conducting and completing the research.*

We anticipate completing the research study in 18 months.

- *Describe your facilities.*

Our research suite includes four individual, private research rooms that each contain a password protected computer and locked file cabinets. The research suite is locked via swipe access that only research staff have access to.

- *Describe the availability of medical or psychological resources that subjects might need as a result of an anticipated consequences of the human research.*

Although the study is expected to cause no more than minimal distress, a resource sheet will be provided to participants with local emergency & referral numbers.

- *Describe your process to ensure that all persons assisting with the research are adequately informed about the protocol, the research procedures, and their duties and functions.*

All research staff are given protocols that outline duties for each job that is part of the study. These protocols are available on an online computer drive which staff members have access to.

